3.1 Study Endpoints

- Baseline plasma and urine fasting choline, phosphatidylcholine (PC), trimethylamine-Noxide (TMAO), trimethylamine (TMA), crotonobetaine and gammabutyrobetaine levels.
 - Changes in levels of non-labeled TMAO, TMA, crotonobetaine, betaine and gammabutyrobetaine over time measured by established techniques by mass spectrometry.
 - Baseline and subsequent (end of study blood draw) changes in platelet function during study.
- Serial changes in plasma and urine (area under curve and percent rise calculations).
 - Correlation with baseline fasting choline, phosphatidylcholine (PC), TMAO, TMA, crotonobetaine and gammabutyrobetaine levels.
- Changes in markers of metabolism (e.g. lipid profile, and other metabolic markers).

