3.0 STUDY DESIGN

This is a prospective non-blinded randomized study with 5 study arms as detailed below. For each study arm, subjects will be asked to consume choline bitartrate tablets, phosphatidylcholine capsules, and/or eggs or egg whites every day for 4 weeks.

Arm 1: whole hardboiled egg

Arm 2: choline bitartrate tablets

Arm 3: whole hardboiled egg + choline bitartrate tablets

Arm 4: egg whites + choline bitartrate tablets

Arm 5: phosphatidylcholine capsules

For arms 1-4, subjects will be randomly assigned to one of these study arms at the time of enrollment. For arm 5, the phosphatidylcholine arm, which we have added in version 1.2 of this protocol, subjects will not be randomized but will instead be assigned this arm until at least 10 subjects have completed this arm. We expect to enroll at least 10 subjects into each of the 5 arms of the study, up to a maximum of 100 total study participants. The large anticipated maximum enrollment accounts for any subjects who may withdraw early or who may need to be withdrawn because of antibiotic usage or non-compliance during the course of the study.

At the first (baseline) study visit, subjects will have blood and urine samples collected. Subjects will then be randomized or assigned to one of the five study arms as described above.

Following randomization, or assignment in the case of arm 5, subjects will be asked to pick up their assigned study food and/or supplements each week. Spot urine collections will be collected weekly. Subjects will also be asked to provide a stool sample at the time of the spot urine collection if they are able to. The stool samples will be optional, we will not require them.

At the day 7 visit and the final visit they will have repeat blood and urine collections. After 4 weeks of supplementation, subjects will have their final study visit. This visit will occur between 26 and 30 days after their baseline visit.

	Day 1 (Baseline)	Day 2	Day 7*	Day 8	Day 14*	Day 21*	Day 28*	Final Visit (Day 29)
Informed consent	Х							
Vital signs and brief medical history	Х		Х				Х	
Fasting Blood Draw	Х		Х				Х	
Pick up eggs and/or supplements		Х	Х		Х	Х		
Spot Urine sample	Х		Х		Х	Х	Х	
Start 24 hour urine	Х		Х				Х	
Return 24-Hour Urine		Χ		Х				Х

|--|

^{*}these study visits can occur +/- 2 days from day noted

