7.0 STATISTICAL PLAN

7.1 Sample Size Determination

Based on previous research, we calculate that a sample size of 5 in each arm will provide us with a power of 0.9 to detect a significant difference between groups at a significance level of 0.05. However, we plan to enroll at least 10 subjects in each arm in order to compensate for any unexpected occurrences or subject dropouts.

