7.2 Statistical Methods

We plan to use standard descriptive statistics to characterize the overall study population and subgroups of interest both at baseline and during follow-up. Summary statistics such as means, medians, standard deviations, and ranges will be produced for measured variables, and compared within and between groups with chi-square, Student t-test/Wilcoxon test, or ANOVA analysis as appropriate. Graphical methods will be used extensively to examine distributions, identify potential influential points, and guide in data transformations if warranted.

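### Correlating an analyte's percent rise with its own single-visit baseline tests the wrong null (section 3.1)

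*Combined protocol and SAP*

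**What the plan says.** Section 3.1 (Study Endpoints) has the item "Serial changes in plasma and urine (area under curve and percent rise calculations" and, set beneath it, the sub-item "Correlation with baseline fasting choline, phosphatidylcholine (PC), TMAO, TMA, crotonobetaine and gammabutyrobetaine levels". The same section makes a separate endpoint of "Changes in levels of non-labeled TMAO, TMA, crotonobetaine, betaine and gammabutyrobetaine over time measured by established techniques by mass spectrometry". TMAO, TMA, crotonobetaine and gammabutyrobetaine appear in both the baseline list and the change list.

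Section 3.0 gives one baseline occasion, "At the first (baseline) study visit, subjects will have blood and urine samples collected", and then "At the day 7 visit and the final visit they will have repeat blood and urine collections". Section 7.2 says that measures will be "compared within and between groups with chi-square, Student t-test/Wilcoxon test, or ANOVA analysis as appropriate", with data transformation if it proves warranted. It names no correlation method and no baseline-adjusted model, and it does not mention the link between a change score and its own baseline.

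**The concern.** Percent rise is, on the usual definition, 100 × (follow-up − baseline) / baseline; the plan gives no formula. Correlating it with baseline puts one measured number, with its error, on both axes. A subject whose single fasting sample happens to be low appears at the left of the plot and also tends to show a large rise. A negative correlation can then appear although the fold response has nothing to do with the subject's true level.

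At stake is a statement that people with low baseline TMAO respond more to choline. Readers could take that as biology, for the trial's central analyte, when arithmetic and regression to the mean may account for it.

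**Working it through.** **The plan's own figure.** The only statistical figure is in section 7.1: "a sample size of 5 in each arm will provide us with a power of 0.9 to detect a significant difference between groups". No effect size or SD is given, so it can only be back-solved: a two-sided t-test with 5 per arm and power 0.9 needs a difference of about 2.35 SD. It does not concern the correlation endpoint.

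**Inputs.** From the documents: one baseline; at least 10 subjects in each of 5 arms, so 5 × 10 = 50; and the 10-fold TMAO rise after choline bitartrate reported in section 1.0. Everything else is assumed: lognormal levels, the stable share s of the log-baseline variance (the rest is within-person and assay noise), and the between-subject spread of the fold response.

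**Built-in correlation.** Let log baseline be T + e0 and log follow-up be T + e1 + d. T is the true level, e0 and e1 are noise, and d is the log fold response, independent of T. Take log-baseline variance as the unit, so that T has variance s and each noise term has 1 − s. Let v be the variance of d in those units. Then:

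- cov(log change, log baseline) = −(1 − s)
- var(log change) = 2(1 − s) + v
- r = −(1 − s) / √(2(1 − s) + v)

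Percent rise increases steadily with log change, so a rank correlation is the same for either, and taking logs removes nothing.

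- With v = 0 this is r = −√((1 − s)/2): −0.59, −0.50 and −0.39 for s = 0.3, 0.5 and 0.7.
- With baseline CV and response CV both 0.5, v = 1. Then s = 0.7 gives −0.3/√1.6 = −0.24, and s = 0.5 gives −0.5/√2 = −0.35.
- With s = 1 (error-free baseline), r = 0.

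**How often a nominal 5% Spearman test is significant** (simulated; response independent of the true baseline):

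| Scenario | n = 50 | n = 10 |
|---|---|---|
| Common fold rise, s = 0.3 / 0.5 / 0.7 | 99% / 95% / 76% | 39% / 29% / 18% |
| Varying fold rise (response CV 0.5, baseline CV 0.5 to 1.0), s = 0.5 to 0.7; significant negative results | 35-86% | 9-23% |
| Three arms at 10-fold and two at 1- to 2-fold, pooled, s = 0.3 to 0.7 | about 25-90% | not applicable |
| Proportional rise, error-free baseline | about 5% | about 5% |

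If instead the absolute rise is unrelated to baseline, median Spearman is −0.67 to −0.86. Percent rise then really is smaller at higher baselines, but only because a similar rise is divided by a larger number. I leave this case out of the quoted range because it is a matter of scale.

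**AUC.** Trapezoid weights for Days 1, 7 and 28 are 3, 13.5 and 10.5. With equal variances and correlation 0.5 between visits:

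- Total AUC against baseline: (3 + 6.75 + 5.25)/√515.25 = 15/22.7 = 0.66.
- Without Day 1: 12/√434.25 = 12/20.8 = 0.58.

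Most of the positive correlation is therefore ordinary tracking between visits.

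**Oldham's method** (log change against the mean of log baseline and log follow-up). Under the model above, cov(change, mean) = v/2, which is positive whenever fold response varies. Over s = 0.5 to 1.0 and baseline CV 0.5 to 1.0, with response CV 0.5, r is +0.15 to +0.45, and false significance at n = 50 is about 17-88%.

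**Slope model.** Regress log follow-up on observed log baseline. If fold response is unrelated to true baseline, the expected slope is s, whatever v is. Divided by s, it is 1. The null is therefore a slope of 1 after correction for baseline error.

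**The case against.** - **The target is inferred.** The sub-item names no outcome, coefficient or test, and section 7.2 lists no correlation test. The link to percent rise rests on layout, which is a weak guide: the same list sets platelet function under baseline metabolite levels. This stands as a limit. The reading remains the natural one, and the ambiguity itself needs repair.
- **The coupling is not universal.** A reader might infer that percent rise is always negatively correlated with its own baseline. It is not: with a proportional rise and an error-free baseline the correlation is zero. One fasting sample will not be error-free, but the documents give no reliability, so the size is unknown.
- **A false finding is not the expected outcome everywhere.** A reader might infer that the trial would probably report one. Within an arm of 10 the rate is below one half throughout the quoted range, and pooling arms with different rises lowers the 50-subject rates.
- **AUC is not a mirror-image artefact.** A reader might infer that AUC is coupled just as strongly in the other direction. The check shows mostly tracking, and the plan does not say whether AUC is total or incremental.
- **The endpoint is minor.** The objective and hypotheses concern before/after and between-arm comparisons in a self-described pilot. This stands and limits the severity. It does not make r = 0 the right null.

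**Conclusion.** The point holds for same-analyte percent-rise correlations, and nothing in section 7.2 corrects for it. Under the assumptions shown, falsely significant results occur in about 35-99% of trials with 50 similar subjects, about 25-90% with pooled arms of differing response, and about 10-40% in one arm of 10. These ranges rest on assumed stable shares of 0.3 to 0.7 and assumed spreads. With an error-free baseline and a proportional rise the rate returns to about 5%.

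A positive correlation of total AUC with baseline would not be evidence about response either. Cross-analyte pairs, such as baseline choline with TMAO rise, are free of coupling only as far as the analytes' baselines are uncorrelated; simulated with unrelated baselines, they gave about 5%.

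A reader might go further and doubt the trial's comparison of arms on TMAO. The documents do not support that, because the comparison does not use this correlation. The change is worth making before analysis, but the design does not depend on it.

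**What to change.** In section 3.1:

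1. Name the variable that is correlated with baseline, and say whether AUC is total or incremental.
2. Drop the same-analyte percent-rise correlations, or report them descriptively without a test of r = 0.
3. If dependence on baseline is a question worth keeping, regress log follow-up on log baseline with arm in the model, and test the slope against 1 with allowance for baseline error. There is only one baseline visit, so show the result over a stated range of reliabilities.
4. Use Oldham's method as a sensitivity analysis only, noting that it is biased positive when fold response varies between subjects.
5. Keep the cross-analyte correlations, within arm or adjusted for arm, with the caveat about correlated baselines.

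The cost is analysis wording and the loss of a simple same-analyte correlation. No new samples, visits or subjects are needed.

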4.0 SUBJECT SELECTION AND WITHDRAWAL

Subjects must meet the following inclusion/exclusion criteria to be eligible for the study.

4.1 Inclusion Criteria

Inclusion criteria:

- Men and women age 18 years or above.
- Willing to remain on aspirin or stay off aspirin or aspirin products for 1 week prior to starting the study and throughout the study period.
- Able to provide informed consent and comply with study protocol.
- Able to be off all other supplements during the study period.

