4.3 Subject Recruitment and Screening

Subjects will be recruited from the Cleveland, OH area. Subjects will be recruited by several methods, including (but not limited to) posted advertisements, chart review, and personal interactions with patients in the cardiology outpatient departments at the

Cleveland Clinic Foundation. All advertising materials used for this study will be approved by the Cleveland Clinic IRB prior to dissemination.

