6.1 Study Visit Procedures

- Blood Draw
- Spot Urine
- Medical History
- Medication Review
- Physical Exam including blood pressure, height, weight, and waist circumference
- 24-hour Urine Collection
- Stool Sample Collection (optional)

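### Platelet-function change is an endpoint in a trial open to both aspirin users and non-users, but Section 7.2 names only unadjusted comparisons; adjusting for aspirin use and baseline would cost almost nothing

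*Combined protocol and SAP*

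**What the plan says.** All references are to the combined protocol and SAP.

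- **Endpoint.** Section 3.1 lists "Baseline and subsequent (end of study blood draw) changes in platelet function during study".
- **Eligibility.** Section 4.1 requires subjects to be "Willing to remain on aspirin or stay off aspirin or aspirin products for 1 week prior to starting the study", and the same condition then runs to the end of the study. Users and non-users may both enter, and each is to hold one status throughout.
- **Recruitment.** Section 4.3 names "personal interactions with patients in the cardiology outpatient departments" among its sources, so aspirin users are plausible. No prevalence is given.
- **Data.** Section 6.1 lists "Medication Review" as a visit procedure. No aspirin variable is named.
- **Allocation.** Section 3.0: "For arms 1-4, subjects will be randomly assigned to one of these study arms at the time of enrollment". No stratification is stated. Arm 5 is filled by assignment, without randomisation.
- **Analysis.** Under Section 7.2, measured variables are to be "compared within and between groups with chi-square, Student t-test/Wilcoxon test, or ANOVA analysis as appropriate". No covariate, ANCOVA or stratified analysis appears. The same section will "characterize the overall study population and subgroups of interest both at baseline and during follow-up", but this is descriptive, and neither aspirin nor any other subgroup is named.

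**The concern.** The eligibility rule controls aspirin within each subject, but nothing in the plan deals with it between subjects. The endpoint is a change from baseline and status is meant to stay fixed, so a constant aspirin effect on platelet level cancels. What can remain is a difference in the size of the change: if aspirin already alters platelet response, users may move more or less than non-users over four weeks. The documents neither establish this nor rule it out.

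If it happens, there are two consequences.

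- **Arms 1-4.** Mixing users and non-users adds unexplained variance to the platelet comparison, and precision falls.
- **Arm 5.** Its share of users is not governed by randomisation, so a systematic difference in aspirin use could bias its contrasts with the other arms.

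**Working it through.** **Inputs from the documents.** At least 10 subjects per arm and a significance level of 0.05 (Section 7.1); four randomised arms and one assigned arm (Section 3.0).

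**Inputs assumed, because the documents do not give them.** Aspirin prevalence *p*, taken as 10-50%; and the difference in mean platelet change between users and non-users, *g*, in within-stratum SDs, taken as 0, 0.5 and 1. Tests are taken as two-sided.

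**The plan's own figure.** Section 7.1 gives 5 per arm for power 0.9. It states no endpoint, effect size, SD or test, so it cannot be reproduced. Under a two-sided t-test it implies a standardised difference of 2.35. It says nothing about platelet function.

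**Step 1: chance imbalance among randomised arms.** Let X and Y be independent Binomial(10, *p*) counts of users in two arms. The middle column is P(|X − Y| ≥ 3), exact. The last column is the chance that the highest and lowest of the four randomised arms differ by 3 or more, by simulation with 200,000 runs.

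| Prevalence | Two arms | Some pair of arms 1-4 |
|---|---|---|
| 10% | 6% | 20% |
| 20% | 16% | 48% |
| 30% | 22% | 60% |
| 50% | 26% | 67% |

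Arm 5 is left out because its aspirin share is not a random draw from the same pool.

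**Step 2: what an imbalance does to one contrast.** The shift is (difference in user share) × *g*. For 3 users in 10 it is 0.3*g*, so 0.15 SD at *g* = 0.5 and 0.3 SD at *g* = 1. For comparison, the standard error of a contrast with 10 per arm is √(2/10) = 0.45 SD, or √(1.21 × 2/10) = 0.49 SD once the variance in Step 3 is included (*p* = 0.3, *g* = 1).

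**Step 3: precision lost among randomised arms.** Ignoring aspirin multiplies the residual variance by 1 + *p*(1 − *p*)*g*². At *p* = 0.3 and *g* = 1 this is 1 + 0.3 × 0.7 × 1 = 1.21. With 10 per arm and a two-sided 0.05 t-test (18 df), power 0.90 needs a standardised difference of 1.53. Dividing that by the square root of the variance factor gives the unadjusted power:

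| Prevalence | *g* = 0 | *g* = 0.5 | *g* = 1 |
|---|---|---|---|
| 20% | 0.90 | 0.889 | 0.853 |
| 30% | 0.90 | 0.885 | 0.838 |
| 50% | 0.90 | 0.882 | 0.826 |

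The 0.90 reference ignores the degrees of freedom that adjustment uses. With 16 df instead of 18, the same calculation gives 0.896, so the benchmark hardly moves.

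**Step 4: validity of the unadjusted test.** Two arms of 10 were simulated with 30% users and *g* = 0.5, 1 and 1.5. The false-positive rate of the unadjusted t-test was about 5% each time (4.8%, 5.1%, 5.0%). Among randomised arms the test therefore keeps its error rate.

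**Step 5: arm 5.** The formula in Step 2 applies, but no probability can be attached to the difference in user share. Part of any shift may be systematic, so more subjects would not remove it.

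**The case against.** The strongest case against has five parts.

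1. **The design already removes most of the problem.** Fixed status and a change score cancel the level effect, and nothing in the documents shows that users and non-users change differently. This stands: the remaining concern is conditional on *g* not being zero.
2. **Randomisation covers arms 1-4.** A reader might infer from the imbalance figures that platelet contrasts among these arms are confounded. The documents do not support that. Chance imbalance is already within the test's error rate (Step 4), and a 0.3 SD shift is smaller than the contrast's own standard error. For these arms the issue is precision. The argument does not extend to arm 5.
3. **Prevalence could be low.** A reader might take an aspirin mix as a fact of this sample. Section 4.1 only permits one. Section 4.3 makes users plausible, while the exclusion of significant chronic illness in Section 4.2 could keep them few. It would also be tempting to quote the imbalance across all five arms, but that treats arm 5 as a random draw.
4. **The model is simple.** If aspirin changes the response to treatment itself, the effect is an arm-by-aspirin interaction, and one additive term captures it only in part. Results split by aspirin status would rest on about 2-3 users per arm at 20-30% prevalence. At 20%, the chance that at least one of four arms of 10 has no more than one user is 85% (48% at 30%). Such a display can only be descriptive. Baseline platelet function may also carry part of the aspirin information, so the gain from the aspirin term on top of baseline is not established.
5. **The endpoint is peripheral.** Platelet function is absent from the objectives in Section 2.0, the principal goal in Section 1.0 is plasma TMAO, and Section 6.0 calls the study a pilot. This limits the importance of the point but does not remove it, because the remedy is so cheap.

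**Conclusion.** The point holds as a minor improvement. Section 7.2 names only unadjusted comparisons for a platelet endpoint in a population that may include aspirin users and non-users. If the two groups change by different amounts, comparisons among arms 1-4 lose some precision: from power 0.90 to about 0.88-0.89 at a 0.5 SD difference and 0.83-0.85 at 1 SD, for prevalence of 20-50%. If they change equally, nothing is lost. Comparisons with arm 5 may in addition be biased, by an amount that the documents do not allow anyone to size. Prevalence and the difference in change are assumptions throughout.

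The documents do not show that the unadjusted test is invalid among the randomised arms, that aspirin users will in fact be enrolled in numbers, or that the TMAO comparison is affected.

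**What to change.** In Section 7.2, prespecify for platelet function an ANCOVA of the end-of-study value (or its change from baseline) with arm, baseline platelet function and aspirin use (yes/no) as terms. With baseline in the model, the end value and the change give the same arm contrasts. Report the number of aspirin users in each arm, arm 5 included. Label any display by aspirin status as descriptive, and note that adjustment reduces but cannot guarantee removal of bias in comparisons with arm 5.

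Aspirin status has to be established at screening to apply Section 4.1, and Section 6.1 already provides for a medication review. Because no aspirin variable is named, a yes/no field should be specified in the case report form. The cost is two degrees of freedom, one for baseline and one for aspirin. No extra visits, samples or subjects are needed, and the rule on aspirin use itself does not change.

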1.0 BACKGROUND AND SIGNIFICANCE

The principal goal for the study is to examine whether there is a difference between the ingestion of choline through supplements versus choline found within eggs on plasma TMAO levels. We have previously shown that dietary intake of trimethylamines, including the choline group of phosphatidylcholine (PC), is mechanistically linked to cardiovascular disease risk and that the metabolism of these trimethylamine nutrients in humans is modulated by the intestinal microbes (gut microbes). Additionally, extensive animal studies link an essential role of gut microbiota to the metabolism of choline and the production of metabolites that promote / accelerate atherosclerotic processes (Wang et al, 2011, Nature). We have also recently shown a 10-fold increase in plasma TMAO levels following supplementation with choline bitartrate supplements. However, another pilot study by a collaborator did not show the same increase in plasma TMAO levels following the ingestion of whole eggs, a major dietary source of choline. Therefore, with this study we wish to examine the differences, if any, between the ingestion of an equivalent mass of total choline in the free form (as bitartrate salt) as a supplement vs. within whole eggs. We also wish to examine the ingestion of an equivalent mass of choline as a phosphatidylcholine (PC) supplement capsule and compare this to the ingestion of the choline bitartrate supplements and/or the whole eggs.

Eggs, and specifically the egg yolk, contain a large amount of total choline (USDA Database for the Choline Content of Common Foods, 2008). However, egg white contains potential antimicrobial peptides that could influence gut microbial composition and function, and therefore impact conversion of choline into TMA and TMAO observed in subjects. Therefore, we hypothesize that the consumption of whole eggs (hardboiled) will not elevate plasma TMAO levels to the same extent as a comparable amount of total choline ingested in capsule form as the choline bitartrate salt. We further hypothesize that the consumption of egg white with choline bitartrate tablets may result in less of a rise in TMAO levels than ingestion of the choline bitartrate supplement alone.

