4.2 Exclusion Criteria

Exclusion criteria:

- Significant chronic illness.
- Active infection or received antibiotics within 1 month of study enrollment.
- Use of OTC probiotic within 1 month of study enrollment.
- Chronic gastrointestinal disorders, such as ulcerative colitis or Crohn's disease.
- Allergy to eggs or lactose.
- Having undergone bariatric procedures or surgeries such as gastric banding or bypass.
- Pregnancy.
- Any condition that, in the judgment of the Investigator, would place a subject at undue risk by being enrolled in the trial or cause inability to comply with the trial.

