5.3 Subject Compliance Monitoring

Subjects will be observed taking their assigned treatment, either eggs or choline supplements, by a study coordinator or other study personnel during their first few visits to ensure the subjects are able to comply with the study procedures. Following this, weekly spot urine collections will be analyzed for choline, phosphatidylcholine (PC),

TMAO, TMA, crotonobetaine, and gammabutyrobetaine levels to ensure that subject levels do not drop from baseline, which would indicate non-compliance with the study treatments.

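### Section 4.1 sets no supplement-free period before the Day 1 baseline, so a recent choline user is eligible and could have a raised baseline TMAO

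*Combined protocol and SAP*

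**What the plan says.** The supplement criterion in Section 4.1 reads "Able to be off all other supplements during the study period". It has no part that applies before the study starts.

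Three other exposures do have a window before the start:

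- Aspirin (Section 4.1): use or non-use is to be held constant "for 1 week prior to starting the study and throughout the study period".
- Antibiotics (Section 4.2), an exclusion: "Active infection or received antibiotics within 1 month of study enrollment".
- Probiotics (Section 4.2), an exclusion: "Use of OTC probiotic within 1 month of study enrollment".

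On timing, Section 3.0 states: "At the first (baseline) study visit, subjects will have blood and urine samples collected". The visit schedule in that section puts informed consent, the fasting blood draw and the first urine collections on Day 1, and shows no screening or run-in visit.

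Section 1.0 reports a "10-fold increase in plasma TMAO levels following supplementation with choline bitartrate supplements". Section 5.3 has weekly spot urine analysed for choline, TMAO and related compounds "to ensure that subject levels do not drop from baseline, which would indicate non-compliance with the study treatments".

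**The concern.** The exposure without a lead-in is the one the trial studies. By the protocol's own account, choline bitartrate can raise plasma TMAO substantially, so a subject who was taking such a product shortly before Day 1 may not give a supplement-free reference value.

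The Day 1 value is used in three places: the before-versus-after objective in Section 2.0; the change, percent-rise and baseline-correlation endpoints in Section 3.1; and the compliance check in Section 5.3. A raised baseline would make the subject's rise look too small. It could also produce an apparent fall in someone who took every dose, and Section 3.0 foresees withdrawing subjects for non-compliance. What is at stake is therefore the accuracy of that subject's change score and, possibly, whether the subject is kept in the study.

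**Working it through.** **Does the text leave the gap?**

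1. The aspirin criterion names the week before the start and the study period separately. In this protocol's usage, then, the study period does not reach back before the start.
2. Consent and the baseline sample are both on Day 1. Even if Day 1 counts as part of the study period, the restriction begins no earlier than the day of the sample.
3. No exclusion in Section 4.2 covers earlier use of choline, phosphatidylcholine or similar products. The brief history on Day 1 (Section 3.0) and the medication review (Section 6.1) do not name supplements, and no rule acts on what they find.
4. The fasting draw limits same-day intake but does not require that supplements were stopped.

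So a recent choline user meets every written criterion.

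**How large could the error be for one subject?**

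Inputs: a true rise of 10-fold (Section 1.0) and a residual baseline inflation *k*. The documents do not give *k*. I assume 2, 5 and 10; 10 is the full reported effect with nothing lost by the time of the sample, so I treat it as an upper bound.

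Observed percent rise = 100 × (10/*k* − 1):

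- no inflation: 100 × (10 − 1) = 900%
- *k* = 2: 100 × (5 − 1) = 400%
- *k* = 5: 100 × (2 − 1) = 100%
- *k* = 10: 100 × (1 − 1) = 0%

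**What does one such subject among 10 do to the arm's mean?**

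The other nine have a log10 change of 1; the affected subject has 1 − log10(*k*). Geometric mean rise = 10^(1 − log10(*k*)/10):

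- *k* = 2: 10^(1 − 0.0301) = 9.3-fold
- *k* = 5: 10^(1 − 0.0699) = 8.5-fold
- *k* = 10: 10^(1 − 0.1) = 7.9-fold

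Mean percent rise = (9 × 900 + affected subject's rise)/10: 850%, 820% and 810%, against 900%.

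**When would the compliance check misread a subject?**

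If the assigned treatment takes the subject to *r* times the supplement-free level, the ratio to the observed baseline is *r*/*k*, which is below 1 when *r* < *k*. In the limiting case of no true rise (*r* = 1) the apparent change is −50%, −80% or −90% for *k* = 2, 5 or 10. Section 1.0 expects whole eggs and phosphatidylcholine to raise TMAO less than bitartrate, so *r* < *k* is possible there. (I name arms by treatment because Sections 3.0 and 5.2 number the egg and tablet arms differently.)

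**Does power suffer?**

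Section 7.1 states 5 per arm for power 0.9 at a significance level of 0.05. This cannot be reproduced: no endpoint, effect size, SD, test or sidedness is given. The point does not dispute it. For scale only, a two-sided t-test with those figures implies a standardised difference of 2.35. Suppose that represents a 10-fold rise against no rise on the log10 scale. In simulation, one subject at *k* = 10 then lowers power from about 0.999 to 0.99 at 10 per arm. Under the same assumptions, power at 5 per arm would fall from 0.90 to about 0.55, but the plan enrols at least 10.

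**The case against.** The strongest reply is that nothing shows the baseline to be raised in fact. A reader might infer that a prior user's baseline is inflated 10-fold and that the change score and compliance check are simply wrong for that subject. The documents do not support this. The 10-fold figure comes without dose, duration or sampling time, and it describes levels following supplementation, not what remains in a fasting sample after stopping. This stands, and it is why the point is worded as a possibility and shown over a range.

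A reader might also infer that one such subject threatens the arm-level result. That does not follow either. The power loss at 10 per arm is small even at the upper bound. In the four randomised arms prior use is balanced in expectation, and equal inflation would cancel from a difference in mean log change. Section 7.2 also compares measured variables between groups during follow-up, and on-treatment levels do not use the baseline. The phosphatidylcholine arm is not randomised, so balance in prior use cannot be assumed there.

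On compliance, a fall on eggs is possible but not established. Eggs themselves supply much choline, Section 5.3 uses urine and several analytes whereas the 10-fold figure is plasma TMAO, and observed dosing at the first visits is a second check.

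Finally, the other windows may have their own reasons: antibiotics and probiotics act on gut microbes, and aspirin bears on the platelet endpoint in Section 3.1. Their lengths need not carry over to choline. That is fair, and it is why no length is proposed here. It does not explain why the study's own exposure has no window at all.

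**Conclusion.** The gap is real, and nothing elsewhere in the document closes it: followed as written, the eligibility rule admits a subject whose reference value could be raised by the exposure under study. The effect on that subject could be large. A true rise of 900% would read as 400%, 100% or 0% at 2, 5 or 10 times residual inflation. The effect on an arm of 10 with one such subject is modest: a geometric mean rise of 9.3-, 8.5- or 7.9-fold instead of 10-fold, with little change in power.

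These figures assume a true 10-fold rise and an inflation that the documents do not state. How many enrollees would be recent choline users is also unknown. The power figures rest further on an SD inferred from a sample size statement that cannot be reproduced, so they indicate scale only. The point supports a cheap improvement to the protocol; it does not support a claim that the trial's comparison is invalid.

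**What to change.** - In Section 4.1, make the supplement restriction start before the baseline sample. The sponsor should set the length of the window and justify it.
- At the Day 1 history, record supplement use in the preceding month, including whether any product contained choline.
- In Section 7.2, add a sensitivity analysis that repeats the TMAO change analysis without subjects who reported choline-containing products.

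The cost is one eligibility line, one history question, one repeat analysis and slightly slower enrolment. If enrolment is already complete, the sensitivity analysis can still be done wherever prior use was recorded.
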